4.3.7 Pharmacokinetic (PK) Analysis Set

The PK analysis set consists of all patients in the SAF with at least 1 post-dose blood sample providing evaluable PK data. The PK analysis set will be used for all PK analyses.

Patients may be removed from the estimation of certain PK parameters on an individual basis depending on the number of available blood samples. These patients will be identified at the time of analysis.

5 Patients Disposition

5.1 Disposition

The number and percentage of patients ongoing treatment, ongoing in the study, patients who died with the corresponding reason for death and whether the death was within 30 days of last dose or not, patients who discontinued treatment with the corresponding reason for drop out and patients who discontinued the study with the corresponding reason for drop out will be tabulated by dose group.

In addition, the number and percentage of patients in each analysis set will be shown (as defined in Section 4.2.1).

Percentages will be based on the number of patients assigned to treatment in the FAS.

Patient disposition data will be presented in a listing for the FAS.

5.2 Protocol Deviations

Compliance with the protocol will be assessed by the number and percentage of patients with important protocol deviations. Important protocol deviations will be identified prior to database lock and will be listed and summarized by category for FAS. The impact of important protocol deviations on the study procedures or the analyses will be classified according to the following rules:

- The important protocol deviation resulted in exclusion from one or more analysis sets (as defined in Section 4.3)
- The important protocol deviation resulted in permanent discontinuation of study treatment
- The important protocol deviation resulted in exclusion from one or more analyses

6 Demographics and Baseline Characteristics

Demographics and baseline characteristics will be presented for FAS.

Qualitative data (e.g. sex) will be tabulated by category while quantitative data (e.g. weight) will be summarized by descriptive statistics.

Demographic data, baseline disease characteristics, and other baseline data will be listed in detail.

6.1 Demographics

Demographic data will be summarized and include age group (18-<50, 50-<65, ≥ 65), sex, race, ethnicity, weight at baseline and height at baseline.

6.2 Baseline Disease Characteristics

ECOG performance status at baseline will be summarized by grade (0 or 1) and a shift table of baseline to worst on-treatment result will be presented.

The latest set of results/values will be used on demographics (e.g. ECOG, height, weight) summary if a subject has different values for different cohorts.

Listing of ECOG performance status at each visit will be presented for the FAS.

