Figure 6-2: Schematic Illustration of a 2-Step IPE Regimen

Rules for the 2-step IPE regimen are as follows:

- The initial target dose level must be a permitted escalation step based on BLRM output and the consensus of the SST
- The initial target dose level must not exceed the 1-step dose-escalation MTD (if established)
- The C1D8 dose level must be at least one dose level below the initial target dose, and must be a dose level that has been evaluated in ≥ 3 patients using a fixed-dose or 1-step IPE regimen, with a decision to escalate based on the BLRM output and SST review of all available relevant data
- Escalation of the target dose in subsequent cohorts may proceed as in the main and 1-step dose escalation:
 - Separate MTD/RP2D may be identified using fixed-dose, 1-step IPE, and 2-step IPE regimens
 - DLT will be attributed to the dose level of the most recently administered dose prior to onset of the DLT (eg, a DLT with onset on C1D4 would be attributed to the C1D1 dose level, while a DLT with onset on C1D10 would be associated to the C1D8 dose level)
- The dose levels for C1D1 and C1D8 remain fixed for all subsequent cohorts
- Patients receiving 2-step IPE must receive the C1D1 and C1D8 doses prior to receiving the target dose
- If a 2-step IPE regimen is evaluated in Phase I, it may be selected for further evaluation in Phase II

An example of how IPE might be implemented is shown in [Figure 6-3](#).

[figure not shown]

Figure 6-3: Representative Escalation Path Incorporating IPE

IPE = intra-patient escalation.

Actual dose levels will be determined using BLRM and must be approved by SST. In this scenario, after 3 patients were enrolled in Cohort 4 and completed DLT evaluation, the recommended next dose per BLRM was 195 mcg. The SST determined that the 195 mcg dose would be better tolerated using a 2-step escalation regimen, and so Cohort 5 was opened with a dose of 30 mcg on C1D1, 100 mcg on C1D8, and 195 mcg as the target dose (weekly starting on C1D15).

In addition, a patient who is enrolled in a lower dose cohort may move to a higher dose cohort once all the following criteria are met:

- The patient has completed at least 3 cycles of treatment
- The patient did not experience any DLT or any \geq Grade 3 treatment-related toxicity
- The patient does not have any ongoing \geq Grade 2 treatment-related toxicity
- The higher dose cohort has completed SST review with a decision to escalate or was determined to be the MTD/RP2D

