9 STATISTICAL METHODS AND DATA ANALYSES

9.1 General Principles

Categorical data will be presented as frequencies and percentages. For continuous data, the mean, standard deviation, median, minimum and the maximum will be presented.

The Phase I study data will be analyzed and reported based on all patient data from the dose escalation up to the time when all Phase I patients have completed at least 6 cycles of treatment or have discontinued study treatment. Data will be listed, summarized, and analyzed by treatment group. Data for the Phase II expansion cohorts will be reported separately, with a data cut off at the point where at least 80% of patients have completed the follow up for disease progression or discontinued the study for any reason. Additional details of data reporting will be outlined in the statistical analysis plan (SAP).

The following rules will be followed for reporting results unless stated otherwise:

- Screen failure patients are those who signed the ICF, but never started the study treatment for any reason. For these patients, the eCRF data collected will not be included in analyses, but will be reported in the clinical study report as separate listings
- Baseline is defined as the last assessment prior to the first dose of treatment received (ie, C1D1 pre-dose)
- For Phase I, all summaries, listings, figures and analyses will be performed by treatment group
- For Phase II, all summaries, listings and figures for primary efficacy analyses and safety analyses will be presented by disease group (NSCLC, urothelial carcinoma, or synovial sarcoma)

Patients from the dose escalation and dose expansion may be pooled for the RP2D. Additional analyses not described here will also be detailed in the SAP.

Unless otherwise stated, missing data will simply be noted as missing on appropriate tables/listings.

Compliance with the protocol will be assessed by the number and proportion of patients with protocol deviations. Protocol deviations will be identified prior to database lock and will be listed and summarized.

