All listings will be sorted for presentation in order of center and patient identification number. Key variables to be displayed on each listing will be: Study phase, center, patient identification number, age, sex, and race.

The following rules will be followed for reporting results unless stated otherwise:

- Screen failure patients are those who signed the ICF, but never started the study treatment for any reason. For these patients, the eCRF data collected will not be included in analyses but will be reported in the clinical study report as separate listing.
- Baseline is defined as the last assessment prior to the first dose of treatment received (e.g. C1D1 pre-dose).
- Tables, listings, and figures will be presented for Phase I and II separately or combined Phase I/II together as appropriate.
- Tables for DLTs will be produced for Phase I and Phase II.
- Visit time points will be presented in the form Cycle x Day y.

Unless otherwise stated in below sections, missing data will not be imputed, but they will simply be noted as missing on appropriate tables/listings.

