4.2.1 Treatment and Disease Groups for Reporting

The Phase I safety data will be listed, summarized, and analyzed overall and by dose group where dose groups may incorporate pooling of dose levels; the exact extent of pooling will be defined after Phase I actual doses administered are known, and is expected to use the Recommended Phase 2 dose (RP2D) as threshold (see **Table 2**).

Patients who enroll in multiple cohorts will be represented once for each cohort and once in the total/overall study columns for summaries that are based on baseline data (e.g. demographics, medical history). Listing will be presented for patients who are escalated to a higher dose.

Table 2 – Potential Phase I Dose Groups

Treatment Group	Dose Group (Label for TLF Reporting)*	Patients included
IMCnyeso < x mcg QW	< RP2D	All Phase I dose escalation cohorts receiving a dose less than RP2D
IMCnyeso = x mcg QW	= RP2D	All Phase I dose escalation cohorts receiving the same dose as RP2D
IMCnyeso > x mcg QW	> RP2D	All Phase I dose escalation cohorts receiving a dose greater than RP2D

* x mcg is the Recommended Phase 2 Dose (RP2D) where x is determined during Phase I and administered IV over 1-2 hours.

In Phase II, patients will be analyzed according to the disease cohorts laid out in **Table 3**.

Table 3 - Phase II Disease Cohorts at RP2D

Cohort	Disease Cohort
Cohort 1	Advanced NSCLC
Cohort 2	Urothelial Cancer
Cohort 3	Synovial Sarcoma

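### For patients moved to a higher-dose cohort, SAP 6.2 puts on-treatment ECOG and weight into a table whose variables are labelled as baseline

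*SAP*

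**What the plan says.** SAP section 4, among its general reporting rules, says: "Baseline is defined as the last assessment prior to the first dose of treatment received", with the pre-dose assessment on Cycle 1 Day 1 as an example. Protocol 9.1 gives the same definition but equates it with that assessment: "Baseline is defined as the last assessment prior to the first dose of treatment received (ie, C1D1 pre-dose").

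SAP 6.1 lists the demographic variables, among them "sex, race, ethnicity, weight at baseline and height at baseline". SAP 6.2 adds that "ECOG performance status at baseline will be summarized by grade (0 or 1"), and then gives the rule at issue: "The latest set of results/values will be used on demographics (e.g. ECOG, height, weight) summary if a subject has different values for different cohorts".

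SAP 4.2.1 explains why a subject might have more than one set of values. For summaries based on baseline data, "Patients who enroll in multiple cohorts will be represented once for each cohort and once in the total/overall study columns". The same section plans a listing of patients escalated to a higher dose.

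Protocol 6.10.1 sets the conditions for moving to a higher-dose cohort. The first is "The patient has completed at least 3 cycles of treatment". The others concern DLTs, related toxicity and the status of the higher cohort.

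**The concern.** A baseline table should describe patients as they entered the trial. For a moved patient, the 6.2 rule replaces the entry values of ECOG and weight with values taken after about three months of IMCnyeso. Moved patients are also a selected group: they had no DLT, no related toxicity of Grade 3 or higher, and no ongoing related toxicity of Grade 2 or higher. The overall column would then mix entry values for most patients with on-treatment values for a few, all under one baseline label. At stake is the accuracy of Table 14.1.3.1 (Phase I demographics and baseline characteristics, Full Analysis Set) and its agreement with other outputs that use true baseline.

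**Working it through.** The plan states no figure for this point, so there is none to reproduce. The check compares the rules and adds simple arithmetic.

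**1. When the later values are taken**
- Inputs: at least 3 completed cycles before a move (protocol 6.10.1); 28 days per cycle (protocol 7.2).
- 3 × 28 = 84 days of treatment, so the move falls on about study day 84 + 1 = 85 at the earliest, counting Cycle 1 Day 1 as day 1 as SAP section 4 does.
- No other route for a treated patient into a second cohort is described. The latest set of values is therefore an on-treatment set.

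**2. Which variables can differ**
- Protocol Table 7-2 schedules weight and ECOG during treatment, so both can differ between cohorts.
- Height has no row in that table. Although 6.2 names it, it would not be expected to change.

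**3. Which columns are affected**

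SAP 6.2 does not say which columns take the latest set. There are two readings:
- All columns take it. On-treatment values then appear in the lower-cohort, higher-cohort and overall columns.
- Each cohort column keeps its own values and only the overall column takes the latest. On-treatment values then appear in the higher-cohort and overall columns.

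The overall column is affected on both readings, because each patient appears there once and one value must be chosen.

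**4. ECOG categories**
- Inclusion criterion 4 requires ECOG 0 or 1 at Screening, so two grades are enough for entry values.
- None of the move criteria in protocol 6.10.1 refers to ECOG. A moved patient could have ECOG 2 or more, and the two-grade summary has no place for that value.

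**5. Size**
- Input: enrollment in SAP Table 1, which is 4 + 3 + 5 + 3 + 5 + 4 = 24 in cohorts 1 to 6, plus 6 planned in cohort 7, giving 30.
- One moved patient is 1/30 = 3.3% of the overall column. Cohorts have 3 to 6 patients, so one patient is 1/6 = 17% to 1/3 = 33% of a cohort of that size.
- Table 1 does not say whether a moved patient is counted in both cohorts. If so, there are fewer than 30 distinct patients and each weighs slightly more than 3.3%.
- Illustration (assumed): if one moved patient of average weight had changed by 5%, the lower bound of Grade 1 in SAP 8.4, mean overall weight would shift by 5%/30 = 0.17%. A 10% change would shift it by 0.33%.

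**6. Agreement with other outputs**
- SAP 8.3 derives creatinine clearance from weight at Cycle 1 Day 1, and SAP 8.4 grades weight change from baseline. For a moved patient, neither would match the weight in the demographics table.

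**The case against.** The strongest reply is that section 4 of the SAP introduces its reporting rules, including the baseline definition, as applying unless stated otherwise, and that 6.2 does state otherwise for one summary. This stands in part. A reader might infer that 6.2 silently overrides the definition; the documents do not support that, because the exception is written out. But a permitted exception does not make the value right: the variables keep their baseline label, and nothing tells the table's reader that some values are on-treatment.

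A second reply is that a new baseline at entry to the higher cohort may be intended, since SAP 7.1 and 7.2.1 speak of the initial Cycle 1 Day 1 dose. That is possible, and it could explain the higher-cohort column. No second baseline is defined, however. One would still follow the first dose received, and it would not describe a patient at study entry in the overall column.

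A third reply is that the entry values remain recoverable, because SAP section 6 lists baseline data in detail and 6.2 lists ECOG at each visit. This is true and limits the harm, but it does not correct the table.

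A stronger reading is also tempting: since 6.2 plans a shift of ECOG from baseline to worst on-treatment, a reader might infer that the later value becomes the baseline there and hides deterioration before the move. The documents do not support this. The rule covers only the demographics summary. The shift table is a separate output (Table 14.3.7.2.1, Safety Analysis Set), and the section 4 definition continues to apply to it and to the change analyses.

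**Conclusion.** The rule in SAP 6.2 is wrong as written. If followed, it places on-treatment ECOG and weight in at least the overall column of a table presented as baseline, and it can produce an ECOG value with no category. This is more than missing detail, because the SAP states which value to use. It rests on one assumption: that the move in protocol 6.10.1 is the only way a subject acquires values for more than one cohort. The documents describe no other.

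The consequence is small. The number of moved patients is not given, so the supportable statement is about 3% of the overall column per patient; a total share for all moved patients would be a guess. The table is descriptive, and no DLT, dose-escalation or response analysis uses it. The correction is desirable rather than essential.

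**What to change.** Replace the sentence in SAP 6.2 with a rule that the demographics and baseline summary uses the last value before the first ever dose of IMCnyeso. Apply it at least in the overall column and preferably in every column, so that each patient has one set of baseline values and the two ECOG grades suffice. Show ECOG and weight at the time of the move separately, labelled as such; the listing of escalated patients in SAP 4.2.1 is a natural place. The shift and change analyses need no change.

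The cost is one sentence in the SAP and a small adjustment to table programming. The values are already collected.

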6.3 Smoking Status

Smoking status (smoker, ex-smoker, or non-smoker) at baseline will be summarized together with demographics characteristics (see Section 6.1).

6.4 Medical History

6.4.1 General Medical History

Relevant prior medical history and current medical conditions will be summarized separately, but they will be listed together. Medical history and current medical conditions will be coded by using the International Conference on Harmonization (ICH) Medical Dictionary for Regulatory Activities (MedDRA) version 20.0.

6.4.2 Cancer History

Cancer history will be described by original cancer disease (melanoma, synovial sarcoma, urothelial carcinoma, NSCLC) and stage (0, I, II, III, IV) at trial entry. The type/location on body will be listed only, where collected for melanoma and sarcoma. Also, the histology will be listed only for NSCLC.

The duration in months of diagnosis [(Date of Screening - Date of Initial Cancer Diagnosis + 1)/30.4375] and duration in months of metastatic disease [(Date of Screening - Date of detection of metastatic disease + 1)/30.4375] will be summarized by descriptive statistics.

For calculating the duration of diagnosis and metastatic disease, incomplete dates of initial cancer diagnosis and dates of detection of metastatic disease will be imputed as follows (where UK and UKN indicate unknown or missing day and month respectively):

- UK-MMM-YYYY: Assume 15-MMM-YYYY. If the month and year are the same as the first dose of study drug month and year, then assume the date of first dose of study drug.
- UK-UKN-YYYY: If the year is prior to the year of first dose of study drug, assume 01-JUL-YYYY of the collected year. If the year is the same as the first dose of study drug year, then assume the date of first dose of study drug.

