7 STUDY SCHEDULE AND ASSESSMENTS

7.1 Pre-Screening and Screening Period Schedule

All patients will be given both a written and verbal description of the study and allowed adequate time to ask questions and decide whether they want to participate. The Investigator (or an appropriate delegate at the Investigator Site) will obtain written consent from each patient prior to commencing any study-related activities or assessments.

Pre-Screening activities may begin once a patient has signed the study IRB/IEC-approved Pre-Screening ICF. During Pre-Screening the patient's HLA-A*02:01, NY-ESO-1, and LAGE-1A status will be determined to establish patient eligibility. Once confirmed HLA-A*02:01-positive **and** NY-ESO-1- and/or LAGE-1A-positive, the patient will be invited to take part in the full study and provided with the main study information sheet.

There is no window for completion of the Pre-Screening activities. Pre-Screening may be performed while the patient is still on another anti-cancer treatment, prior to experiencing disease progression.

Screening must be completed within 21 days of C1D1; baseline radiological evaluations must be performed within 28 days prior to C1D1. Laboratory and radiological assessments performed as part of standard of care prior to signing the ICF may be used if performed within the Screening window. Screening assessments must be repeated if performed outside of the specified Screening window. Patients may re-screen after abnormal labs or symptoms are corrected or treated, but these should first be discussed and agreed with the Sponsor.

The schedule of assessments for Pre-Screening and Screening is shown in [Table 7-1](#).

Table 7-1: Schedule of Pre-Screening and Screening Assessments

Procedure	Pre-Screening	Screening
Days (relative to first dose)		-21 to -1
Informed consent	X	X
HLA-A*02:01 testing	X	
NY-ESO-1 / LAGE-1A testing (archival or new biopsy)	X	
Demography		X
Inclusion/exclusion criteria		X
Medical history and cancer history		X
Prior anti-cancer therapy		X
Prior/concomitant medications		X
Adverse events		X
Safety Assessments		
Complete physical examination		X
Height and weight		
ECOG performance status		X
Vital signs (body temperature, pulse, respiratory rate, blood pressure, and oxygen saturation)		X
12-lead ECG (triplicate)		X
Hematology panel		X
Chemistry panel		X
Coagulation		X
Urinalysis		X
Thyroid function		X
Serum pregnancy test (women of childbearing potential)		X

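### SAP 6.4.2 sets same-month and same-year partial diagnosis or metastasis dates to the first-dose date, after Screening, so those durations come out zero or negative

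*SAP*

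**What the plan says.** SAP 6.4.2 defines two baseline durations, both ending at Screening. The one for metastatic disease is computed as "Date of Screening - Date of detection of metastatic disease + 1)/30.4375". Time since diagnosis uses the same formula, starting from the initial diagnosis instead. Both are to be summarised with descriptive statistics.

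For incomplete event dates the same section gives four branches:

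- Day missing, default: "UK-MMM-YYYY: Assume 15-MMM-YYYY".
- Day missing, month and year equal to those of first dose: "If the month and year are the same as the first dose of study drug month and year, then assume the date of first dose".
- Day and month missing, earlier year: "If the year is prior to the year of first dose of study drug, assume 01-JUL-YYYY of the collected year".
- Day and month missing, same year as first dose: "If the year is the same as the first dose of study drug year, then assume the date of first dose of study drug".

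Protocol 7.1 states that "Screening must be completed within 21 days of C1D1", and Table 7-1 gives the Screening window as Day -21 to Day -1. The SAP has no cap at the Screening date and no rule for a duration of zero or less. SAP Section 12 does not mention the point.

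**The concern.** The formula ends at Screening, but two of the four branches place the start of the interval at first dose, which comes later. The interval then runs backwards. The same first-dose sentences appear in SAP 7.1 for medication start dates. They make sense there, because the purpose is to sort medications into prior and concomitant relative to first dose. Here first dose is not the reference date of the calculation.

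At stake is the accuracy of the Cancer History table (Table 14.1.5.1 in the SAP's list of planned outputs). The first-dose branches err in one direction only, making disease look more recent than it is. In small cohorts one such patient sets the reported minimum at zero or below and pulls down the mean.

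**Working it through.** The plan states no figure on this point, so there is none to reproduce. The check applies the SAP formula to each branch.

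**Inputs**
- Duration in months = (Screening date − event date + 1)/30.4375 (SAP 6.4.2).
- Screening on Day -21 to Day -1 (Protocol Table 7-1), with the day before first dose counted as Day -1 (SAP Section 4).
- Cohort sizes from SAP Table 1: 3 to 6 patients, two cohorts of 5, 30 in total including 6 planned.

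**First-dose branches.** With the event date set to first dose and Screening k days earlier, duration = (−k + 1)/30.4375.
- Day -1: 0/30.4375 = 0.00
- Day -7: −6/30.4375 = −0.20
- Day -14: −13/30.4375 = −0.43
- Day -21: −20/30.4375 = −0.66

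Evaluating every first-dose date in 2020 against every Screening day from -21 to -1 gave the same range, −0.66 to 0.00, with no positive value.

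**Size of the understatement.** The Screening date cancels, so the error is (first-dose date − true event date)/30.4375.
- Same-month branch, worst case (event on the 1st, dose on the 31st): 30/30.4375 = 0.99 months.
- Same-year branch, worst case (event 1 January, dose 31 December, leap year): 365/30.4375 = 11.99 months.

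**15th-of-month default.** This can fail when the event month is the Screening month, Screening falls before the 15th, and first dose is in the next month. Because first dose is at most 21 days after Screening, the earliest Screening day that works is the 8th (28-day February), 9th (29-day February), 10th (30-day month) or 11th (31-day month).
- Screening on the 8th: (8 − 15 + 1)/30.4375 = −6/30.4375 = −0.20
- Screening on the 14th: (14 − 15 + 1)/30.4375 = 0.00

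In 2020, a leap year, the worst value was −5/30.4375 = −0.16.

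**1 July default.** This applies to years before the first-dose year and stays positive. In the 2020 run the smallest value was 5.39 months (Screening on 11 December, first dose on 1 January: 164/30.4375).

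**A hypothetical extreme.** Metastasis in February with only the year recorded, Screening on 1 November, first dose on 15 November.
- True value: 247/30.4375 = 8.1 (end of February) to 274/30.4375 = 9.0 (1 February).
- Rule: −13/30.4375 = −0.43.
- Error: 8.1 + 0.43 = 8.5 to 9.0 + 0.43 = 9.4 months.
- Effect on the mean of 5 patients: 8.5/5 = 1.7 to 9.4/5 = 1.9 months lower.
- Effect on the mean of all 30 patients: about 0.3 months lower.

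**The case against.** The strongest objection is that this is rare and does little harm. The first-dose branches apply only when the recorded year, or month and year, equals that of first dose. Phase I patients must have relapsed from, be refractory to, or be intolerant of all available therapy classes, and Phase II patients need specified prior therapy (Protocol 5.2). An initial diagnosis in the dosing year with its month unknown should therefore be unusual. No hypothesis is tested, no endpoint or decision rule uses these durations, and a negative value would stand out in the listings. All of that stands and limits the weight of the point. It does not rescue the rule, which gives a non-positive value every time a first-dose branch is used.

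Several stronger readings are tempting, but the documents do not support them:

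- That all partial dates go to first dose. They do not; other partial dates go to the 15th or to 1 July.
- That the 15th-of-month default fails for any early-month Screening. Screening on the 5th, for instance, puts first dose no later than the 26th of the same month (5 + 21 = 26), so the configuration cannot arise.
- That a shift of nearly 2 months in a cohort mean is typical. It needs a year-only date, an early-year event, late-year dosing and a cohort of 5. SAP 4.3.2 also allows pooled dose groups, where the shift is smaller. The median need not move at all.
- That the error misstates how heavily pre-treated patients are. SAP 6.5 describes that through lines of therapy. Its count also uses the metastasis date, but 6.4.2 limits this imputation to the two durations, and the SAP does not say that the imputed date carries over.
- That every non-positive value is impossible. Metastasis could first be seen on a scan within the Screening period, and the Date of Screening is not defined.

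**Conclusion.** The point holds for partial dates that match the first-dose year, or the first-dose month and year. Each gives a duration of −0.66 to 0 months and understates the true value by up to about 1 month (same month) or about 12 months (same year). The default to the 15th adds a narrow second route to values between 0 and about −0.2 months.

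The −0.66 limit assumes that the Date of Screening lies within Day -21 to Day -1. If it were taken from the 28-day imaging window, the limit would be −27/30.4375 = −0.89; a Pre-Screening date, which has no window, could push it lower still. The documents do not say how many patients are affected. Few are likely, mainly through the metastasis date, and the number could be zero. The consequence is confined to a descriptive baseline table. This is a minor correction, worth making because the rule is wrong as written and easy to repair.

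**What to change.** In SAP 6.4.2, replace the first-dose anchor with Screening and state that no date is imputed later than the Date of Screening.

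- For a partial date in the Screening month or year, impute the midpoint between the first day of that month or year and the Screening date.
- For the metastasis date, if a complete initial diagnosis date falls after that first day, use it as the lower bound. If the diagnosis date is itself partial, keep the first day of the known month or year.
- Keep the 15th and 1 July for months or years before that of Screening.

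It would also help to say which recorded date counts as the Date of Screening.

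In the hypothetical above, taken in a non-leap year, 1 January to 1 November is 304 days. The midpoint lies 152 days before Screening and gives (152 + 1)/30.4375 = 5.0 months instead of −0.43. The cap alone guarantees at least 1/30.4375 = 0.03 months; the midpoint is one reasonable choice above that floor.

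The cost is a short SAP wording change and minor programming. No data collection changes.
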